11.2 Serious Adverse Experiences (SAE)

An SAE is defined as any AE occurring at any dose that results in any of the following outcomes:

- death
- a life-threatening adverse experience
- inpatient hospitalization or prolongation of existing hospitalization
- a persistent or significant disability/incapacity
- a congenital anomaly/birth defect

Other important medical events may also be considered an SAE when, based on appropriate medical judgment, they jeopardize the participant or require intervention to prevent one of the outcomes listed above.

11.2.1 Serious Adverse Experience Reporting

The study site will document all SAEs that occur (whether or not related to study drug) on an SAE Report Form. The collection period for all SAEs will begin after informed consent is obtained and end after procedures for the final study visit have been completed.

Reporting of an SAE via SAE Report Form must be (1) sent to the site investigator, (2) reviewed by the site investigator and (3) sent to the study chair and scientific director of AADI **within one business day** of the site learning of the event. The study site will send the SAE report by email (electronic or scanned copy). When available or requested, follow-up information shall be reported via the SAE Report Form and sent to the site investigator and to the study chair and scientific director of AADI.

In accordance with the standard operating procedures and policies of the local Institutional Review Board (IRB) and federal regulations, the site investigator will report SAEs to the IRB.

11.3 Medical Monitoring

It is the responsibility of the Principal Investigator to oversee the safety of the study at his/her site. This safety monitoring will include careful assessment and appropriate reporting of adverse events as noted above, as well as the construction and implementation of a site data and safety-monitoring plan. Medical monitoring will include a regular assessment of the number and type of serious adverse events.

11.4 Monitoring suspected toxicities for discontinued participants

Participants whose treatment is permanently discontinued due to an adverse event or abnormal laboratory value suspected to be related to ABI-009 must be followed at least weekly until the adverse event or abnormal laboratory resolves or returns to grade 1. If a participant requires a dose delay of ≥ 3 weeks from the intended day of the next scheduled dose, then the participant must be discontinued from the study.

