8.6 Dose Modification or Discontinuation of Study Drug

For participants who are unable to tolerate the protocol-specified dosing schedule secondary to DLT, dose adjustments are permitted in order to keep the participant on study drug. If administration of ABI-009 must be interrupted due to DLT, drug dosing will be interrupted or modified according to rules described in the table below. Toxicity will be assessed using the NIH/NCI Common Terminology Criteria for Adverse Events, version 5.0. If a participant requires a dose delay of ≥ 3 weeks from the intended day of the next scheduled dose, then the participant must be discontinued from the study or may resume only with the approval of the Principle Investigator.

Table 4: Hematological and non-hematological toxicities and ABI-009 dosing adjustments

TOXICITY	ACTIONS
Non-hematological toxicity	
Grade 2	If the toxicity is tolerable to the participant, maintain the same dose. If

(pneumonitis management detailed separately in 8.7.4)	the toxicity is intolerable to participant, interrupt ABI-009 until recovery to grade 1 or better. Then reintroduce ABI-009 at same dose. If event returns to intolerable grade 2, then interrupt ABI-009 until recovery to grade 1 or better. Then reintroduce ABI-009 at the lower dose level (refer to Table 3). Reintroduction of ABI-009 may occur once.
Grade 3 (except hyperlipidemia*) (pneumonitis management detailed separately in 8.7.4)	Interrupt ABI-009 until recovery to grade 1 or better. Then reintroduce ABI-009 at the lower dose level. For pneumonitis consider the use of a short course of corticosteroids. Reintroduction of ABI-009 may occur once.
Grade 4	Discontinue ABI-009.
Hematological toxicity	
Grade 2 Thrombocytopenia (platelets <75, $\geq 50 \times 10^9/L$)	Interrupt ABI-009 until recovery to grade 1 or better ($>75 \times 10^9/L$). Then reintroduce ABI-009 at initial dose. If thrombocytopenia again returns to grade 2, interrupt ABI-009 until recovery to grade 1 or better. Then reintroduce ABI-009 at the lower dose level (refer to Table 3). Reintroduction of ABI-009 may occur once.
Grade 3 Thrombocytopenia (platelets <50, $\geq 25 \times 10^9/L$)	Interrupt ABI-009 until recovery to grade 1 or better (platelets $\geq 75 \times 10^9/L$). Then resume ABI-009 at one dose level lower. If grade 3 thrombocytopenia recurs, discontinue ABI-009.
Grade 4 Thrombocytopenia (platelets <25 $\times 10^9/L$)	Discontinue ABI-009.

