Grade 3 Neutropenia (neutrophils <1, $\geq 0.5 \times 10^9/L$)	Interrupt ABI-009 until recovery to grade 1 or better (neutrophils $\geq 1.5 \times 10^9/L$). Then resume ABI-009 at the initial dose. If ANC again returns to Grade 3, hold ABI-009 until the ANC $\geq 1.5 \times 10^9/L$. Then resume ABI-009 dosing at the lower dose level (refer to Table 3). Discontinue participant from study drug for a third episode of grade 3 neutropenia.
Grade 4 Neutropenia (neutrophils <0.5 $\times 10^9/L$)	Interrupt ABI-009 until recovery to grade 1 or better (neutrophils $\geq 1.5 \times 10^9/L$). Then resume ABI-009 at the lower dose level (refer to Table 3). If grade 3 or grade 4 neutropenia occurs despite this dose reduction, discontinue ABI-009.
Grade 3 febrile neutropenia (not life-threatening)	Interrupt ABI-009 until resolution of fever and neutropenia to grade 1 or better. Hold further ABI-009 until the ANC $\geq 1,500/\text{mm}^3$ and fever has resolved. Then resume ABI-009 at the lower dose level (refer to Table 3). If febrile neutropenia recurs, discontinue ABI-009.
Grade 4 febrile neutropenia (life-threatening)	Discontinue ABI-009.
Any hematological or non-hematological toxicity requiring interruption for ≥ 3 weeks	Discontinue ABI-009.

*Grade 3 hyperlipidemia (hypercholesterolemia and/or hypertriglyceridemia) should be managed using medical therapies.

All interruptions or changes to study drug administration must be recorded.

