8.7.4 Management of non-infectious pneumonitis

Non-infectious pneumonitis is a class effect of rapamycin derivatives. Cases of non-infectious pneumonitis (including interstitial lung disease) have also been described in participants taking mTOR inhibitors. Some of these have been severe and on rare occasions, a fatal outcome was observed.

A diagnosis of non-infectious pneumonitis should be considered in participants presenting with nonspecific respiratory signs and symptoms such as hypoxia, pleural effusion, cough or dyspnea, and in whom infectious, neoplastic and other non-medicinal causes have been excluded by means of appropriate investigations. Participants should be advised to report promptly any new or worsening respiratory symptoms. Participants who develop radiological changes suggestive of non-infectious pneumonitis and have few or no symptoms may continue mTOR inhibitor dosing without dose alteration. If symptoms are moderate (Grade 2), consideration should be given to interruption of dosing until symptoms improve. The use of corticosteroids may be indicated. mTOR inhibitor may be reintroduced once at a reduced dose until recovery to Grade 1 or better. For cases where symptoms of non-infectious pneumonitis are severe (Grade 3), mTOR inhibitor dosing should be discontinued and the use of corticosteroids may be indicated until clinical symptoms resolve. Dosing with mTOR inhibitors may be re-initiated at a reduced dose depending on individual clinical circumstances.

Table 5. Pneumonitis Management and ABI-009 Dosing

Pneumonitis Grade	Required Investigations	Management of Pneumonitis	ABI-009 Dose Adjustment
Grade 1	CT scans with lung windows and pulmonary function testing including spirometry, DLCO, and room air O ₂ saturation at rest. Repeat chest x-ray/CT scan every 2 cycles until return to baseline.	No specific therapy required.	Administer 100% of ABI-009 dose
Grade 2	CT scans with lung windows and pulmonary function testing including spirometry, DLCO, and room air O ₂ saturation at rest. Repeat chest x-ray/CT scan every cycle until return to baseline. Consider bronchoscopy.	Symptomatic therapy. If cough is troublesome prescribe corticosteroids.	Reduce ABI-009 dose until recovery to \leq Grade 1. ABI-009 may also be interrupted if symptoms are troublesome. Participants will be withdrawn from the study if they fail to recover to \leq Grade 1 within 3 weeks.

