12 DISCONTINUATION AND REPLACEMENT OF PARTICIPANTS

12.1 Early Permanent Discontinuation of ABI-009 Dosing

A participant may be permanently discontinued from ABI-009 dosing at any time if the participant, the investigator, or the Sponsor feels that it is not in the participant's best interest to continue. The following is a list of possible reasons for early permanent discontinuation of study treatment:

- Participant or participant's legal representative decision
- Protocol violation
- C-SSRS serious suicidal ideation score is increased to a 4 rating
- Death
- Pregnancy
- Refusal to complete patient diary, QOLCE, NCBRF, or C-SSRS questionnaires

If a participant is permanently discontinued from dosing early due to an adverse event, the participant will be followed and treated by the Investigator until the abnormal parameter or symptom has resolved or stabilized.

All participants who permanently discontinue study dosing early should come in for an early permanent discontinuation of study treatment visit as soon as possible and complete all remaining scheduled visits and procedures.

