15.4 Analysis of Primary Endpoint – Tolerability (Study Drug Discontinuation and Compliance)

The proportion of participants permanently discontinuing study drug will be tabulated by treatment group. Drug discontinuation events will be categorized as: (1) Permanently discontinued study drug and (2) Permanently discontinued study drug and withdrew from study. The reason for permanent drug discontinuation will be summarized.

Treatment compliance will be assessed via compliance with scheduled weekly infusions.

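### A dose delay of three weeks or more has three incompatible consequences, and the passage followed decides whether the participant counts as withdrawn in the primary tolerability endpoint

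*Combined protocol and SAP*

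**What the plan says.** Three places state what follows a delay or interruption of 3 weeks or more:

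- Section 8.6, text: the participant "must be discontinued from the study or may resume only with the approval of the Principle Investigator".
- Section 8.6, Table 4, last row: for any "toxicity requiring interruption for ≥ 3 weeks", the action is to stop ABI-009. The row mentions neither leaving the study nor an approval route.
- Section 11.4: "then the participant must be discontinued from the study". The delay is defined as in the Section 8.6 text, but there is no approval route.

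A fourth place has a 3-week limit with a different trigger. Table 5 in Section 8.7.4 says, for grade 2 and again for grade 3 pneumonitis, "Participants will be withdrawn from the study if they fail to recover to" grade 1 or better within 3 weeks.

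Section 12.1 has no delay rule. It says what follows once dosing has stopped early for good: a discontinuation visit, after which the participant should "complete all remaining scheduled visits and procedures".

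On the analysis side, withdrawal from the study, whether voluntary or medically determined, is a primary tolerability endpoint (synopsis, Sections 3.1 and 5.1). Section 15.4 sorts drug discontinuations into two categories: drug stopped, and "Permanently discontinued study drug and withdrew from study".

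**The concern.** A site with a participant three weeks late for a dose can follow the protocol correctly in three ways: take the participant off study, stop the drug and keep the participant in follow-up, or obtain approval and resume. Section 8.6 disagrees with its own table, and Section 11.4 repeats the Section 8.6 rule without its exception.

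Study withdrawal is itself counted as a primary endpoint. If the route into that count depends on which page was consulted, the tolerability result partly reflects how the protocol was read. The same choice decides who remains under observation through the 90-day follow-up and who can enter the per-protocol set.

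**Working it through.** **No stated figure to reproduce.** Nothing in the plan is calculated from this rule, and Section 15.6 bases the 18 participants on feasibility and the 3+3 design. The check is a comparison of texts, followed by simple proportions.

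**The rules side by side**

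| Place | Trigger and clock | Consequence | Section 15.4 category |
|---|---|---|---|
| 8.6 text, approval given | Delay of 3 weeks or more, counted from the day the next dose was due | Dosing resumes | Neither |
| 8.6 text, approval not given | Same | Off study | Drug stopped and withdrew |
| Table 4, last row | Toxicity needing an interruption of 3 weeks or more; start of count not stated | Drug stopped; 12.1 follow-up applies | Drug stopped |
| 11.4 | As in 8.6 text | Off study, no exception | Drug stopped and withdrew |
| Table 5, grade 2 or 3 pneumonitis | No recovery to grade 1 or better within 3 weeks | Withdrawn from study | Drug stopped and withdrew, if doses remained |

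The three delay rules give three distinct consequences. Table 5 shares the Section 11.4 consequence but not its trigger. It also overlaps Table 4, whose last row covers any non-hematological toxicity.

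**Effect on the withdrawal proportion.** One reclassified participant moves it by 1/n. With a maximum of 18 (Section 15.6) and cohorts of 3 (Section 4.1):

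- n = 18: 1/18 = 5.6 points
- n = 12: 1/12 = 8.3 points
- n = 9: 1/9 = 11.1 points
- n = 6: 1/6 = 16.7 points
- n = 3: 1/3 = 33.3 points

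At n = 18 the exact (Clopper-Pearson) 95% intervals are 0 to 18.5% for 0 withdrawn and 0.1 to 27.3% for 1 withdrawn.

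**Chance that the case arises.** The documents give no rate, so this is an assumption shown over a range. With p the chance that a participant has such a delay, the chance of at least one among 18 is 1 − (1 − p)^18:

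- p = 2%: 30.5%
- p = 5%: 60.3%
- p = 10%: 85.0%
- p = 20%: 98.2%

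**Per-protocol set.** Section 15.1.1 requires more than 80% of doses. Of 3 doses, 2/3 = 66.7% fails and 3/3 = 100% passes, so all 3 are needed. A participant who resumes and finishes can qualify if there is no major violation; one stopped before dose 3 cannot.

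**Follow-up at stake.** Doses are 7 days apart, so a 3-week delay is complete 7 + 21 = 28 days after the last dose received. Taking the exit at that point:

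- Counting the 90 days from the last dose received leaves 90 − 28 = 62 days.
- Counting from the planned third dose (day 14 after dose 1), follow-up ends on day 14 + 90 = 104. A delay before dose 2 is complete on day 28, leaving 76 days. A delay before dose 3 is complete on day 7 + 28 = 35, leaving 69 days.

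**The case against.** The strongest reply is that the scope is narrow. Only a delay before dose 2 or dose 3 can trigger the rule, because no dose is due after the third. Between Table 4 and Section 11.4 the total who permanently stop the drug is the same; only the split between the two categories changes. Section 15.4 is a descriptive tabulation with reasons, without a test or threshold. Dose-limiting toxicity and the MTD follow grade, attribution and counts (Sections 8.5 and 4.1), not this rule. All of this stands and limits the consequence.

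One could also say that Section 11.4 uses leaving the study loosely for leaving the drug, since its first sentence concerns stopped treatment. That would bring it closer to Table 4, but it would not supply the approval route in Section 8.6. It would also leave a primary endpoint resting on a guess at the meaning, in a plan whose Section 15.4 separates the two events.

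Three stronger readings are tempting, and the documents do not support them:

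- A reader might count Section 12.1 as a fourth conflicting consequence. It states no delay rule and describes only what follows stopping.
- A reader might infer that the participants with the worst toxicity are the ones lost. Table 4 stops the drug outright for grade 4 non-hematological toxicity, grade 4 thrombocytopenia and grade 4 febrile neutropenia. Those participants need not reach the delay rule and come under Section 12.1.
- A reader might infer that the full 90 days and all later C-SSRS and quality-of-life data are lost. About 28 days have already passed. Section 11.4 requires at least weekly follow-up of suspected related toxicity when treatment is permanently stopped for it, Section 10.7 collects C-SSRS, QOLCE and NCBRF once at discontinuation, and Section 12.3 encourages a final visit. What may be lost is the remaining diary and the remaining scheduled assessments.

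**Conclusion.** The contradiction is real and lies in the current text. A delay or interruption of 3 weeks or more leads to three incompatible outcomes across the Section 8.6 text, Table 4 and Section 11.4. Table 5 adds a separate pneumonitis rule on another clock.

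The effect is a possible misclassification of 5.6 points per affected participant in the overall withdrawal proportion and 33 points in a cohort of 3. Per-protocol membership and the completeness of late follow-up can change as well.

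These sizes assume the full 18 participants and cohorts of 3. How many participants would be affected cannot be known from the documents. The point concerns the clarity of a primary endpoint count and does not bear on dose escalation or the MTD.

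**What to change.** Amend Section 8.6, Table 4, Table 5 and Section 11.4 so that one consequence and one clock are stated. If the pneumonitis rule is meant to differ, say so and say which rule applies where they overlap. State how the chosen rule fits with the follow-up in Section 12.1.

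In the SAP that Section 15.1 promises, assign the case to a Section 15.4 category, and say where a participant who resumes with approval is counted if that route is kept. Section 15.4 already separates stopping the drug from leaving the study, so no new outcome is needed.

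Which discontinuation rule to adopt is for the investigators to decide. The cost is amendment wording and a line in the SAP.

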12 DISCONTINUATION AND REPLACEMENT OF PARTICIPANTS

12.1 Early Permanent Discontinuation of ABI-009 Dosing

A participant may be permanently discontinued from ABI-009 dosing at any time if the participant, the investigator, or the Sponsor feels that it is not in the participant's best interest to continue. The following is a list of possible reasons for early permanent discontinuation of study treatment:

- Participant or participant's legal representative decision
- Protocol violation
- C-SSRS serious suicidal ideation score is increased to a 4 rating
- Death
- Pregnancy
- Refusal to complete patient diary, QOLCE, NCBRF, or C-SSRS questionnaires

If a participant is permanently discontinued from dosing early due to an adverse event, the participant will be followed and treated by the Investigator until the abnormal parameter or symptom has resolved or stabilized.

All participants who permanently discontinue study dosing early should come in for an early permanent discontinuation of study treatment visit as soon as possible and complete all remaining scheduled visits and procedures.

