8.4.1 Dosage/Dosage Regimen

All participants receive study drug every 5-9 days for 3 weeks.

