8.5 Dose-Limiting Toxicities

Definition of Dose Limiting Toxicity (DLT):

Any grade 3 or higher toxicity and designated by the principle investigator as definitely or probably related (level of attribution) to the study drug, and occurring within 30 days of study drug dosing, or as specified per toxicity in the protocol.

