9.1.13 Columbia-Suicide Severity Rating Scale (C-SSRS)

The C-SSRS is a suicidal ideation and behavior rating scale to identify risk in participants. The questionnaire will be given at the end of the 1-month baseline phase, at the end of the 3-week treatment phase, and again at the end of the 3-month follow-up period. Participant serious suicidal ideation scores must remain below a 4 in order to stay on study.

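### No C-SSRS is scheduled while Dose 2 or Dose 3 could still be withheld, and Sections 9.1.13 and 12.1 attach different consequences to a score of 4

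*Combined protocol and SAP*

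**What the plan says.** **When the scale is given.** Section 9.1.13 sets the times: "The questionnaire will be given at the end of the 1-month baseline phase, at the end of the 3-week treatment phase", and again when the three-month follow-up closes. Section 3.1, the visit lists in Sections 10.3 to 10.7 and the Appendix 1 schedule agree with this. The procedures for Visits 3, 4 and 5 (Doses 1 to 3) in Section 10.4 do not include it.

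**What the score is used for.** A serious-ideation score that stays below 4 is listed under tolerability in the primary endpoints (Section 5.1). Section 3.1 also makes the scale part of the safety assessment that determines the MTD.

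**What a 4 leads to.** Section 9.1.13 states: "Participant serious suicidal ideation scores must remain below a 4 in order to stay on study". Section 12.1 says a participant may be taken off dosing and lists possible reasons, one being that the "C-SSRS serious suicidal ideation score is increased to a 4 rating". It then asks those who stop dosing early to attend a discontinuation visit and "complete all remaining scheduled visits and procedures".

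**How stopping is counted.** Withdrawal from study is a primary tolerability endpoint. Section 15.4 adds: "Drug discontinuation events will be categorized as: (1) Permanently discontinued study drug and (2) Permanently discontinued study drug and withdrew from study".

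**The concern.** A numerical stopping criterion works as a scheduled safeguard only if the number is collected while there is still a dose to withhold. Section 10.4 does this for other criteria: oximetry must exceed 93 for the visit to proceed, and a blood count is taken at each dosing visit, which serves the platelet and neutrophil rules in Section 8.6. The C-SSRS has a threshold and primary-endpoint status but no such check.

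The two rules for a score of 4 also pull apart in two ways. One is mandatory and the other discretionary. One concerns remaining in the study and the other concerns dosing only. At stake are the count of participants withdrawn from study and the safety follow-up of a participant with a serious psychiatric signal. Section 12.4 does not replace anyone who withdraws after a first dose.

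**Working it through.** The plan states no figure on this point to reproduce. The check is a reading of the schedule plus simple interval arithmetic.

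**1. C-SSRS schedule against dosing (Sections 10.3 to 10.7, Appendix 1)**

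- Visit 2, end of baseline: scheduled. It may fall on the day of Dose 1, and is pre-exposure.
- Visits 3, 4, 5 (Doses 1, 2, 3): not scheduled.
- Visit 6, one week after Dose 3: scheduled, with no dose left to withhold.
- Visits 7 and 8: not scheduled.
- Visit 9: scheduled.
- Early-discontinuation visit: scheduled, but it follows the decision to stop.

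Scheduled scores between Dose 1 and Dose 3: 0.

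**2. Time from first exposure to first scheduled score**

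Section 8.4.1: "All participants receive study drug every 5-9 days for 3 weeks", nominally 7 days apart. Visit 6 is 7 ± 2 days after Dose 3, so 5-9 days.

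- Dose 1 to Dose 3: nominal 7 + 7 = 14 days; range 5 + 5 = 10 to 9 + 9 = 18.
- Dose 1 to Visit 6: nominal 7 + 7 + 7 = 21 days; range 5 + 5 + 5 = 15 to 9 + 9 + 9 = 27.

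These ranges assume no dose delays for toxicity.

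**3. Doses given without a scheduled post-exposure score**

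Two per participant who completes the course. At full enrolment, 18 × 2 = 36 of 18 × 3 = 54 infusions. This counts opportunities, not expected events.

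**4. A 4 first seen at Visit 6, with Section 9.1.13 applied literally**

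Days are counted from Dose 3 (assumption).

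- Visit 9 falls at 90 ± 7, so days 83-97. Visit 6 falls at day 7 (5-9).
- Follow-up lost: nominal 90 − 7 = 83 days; range 83 − 9 = 74 to 97 − 5 = 92. This is a ceiling of three visits (7, 8, 9).
- Section 8.5 counts a DLT as "occurring within 30 days of study drug dosing". Window remaining after Visit 6: nominal 30 − 7 = 23 days; range 30 − 9 = 21 to 30 − 5 = 25.

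**5. Effect on the endpoints**

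- Withdrawn from study: one such participant is counted as withdrawn under 9.1.13 and not under 12.1, a difference of 1/18 = 5.6 percentage points at full enrolment.
- Section 15.4: both categories require permanent discontinuation of study drug. After three completed doses neither applies. The split matters only for a 4 found before dosing ends, for example on an unscheduled C-SSRS. Then 9.1.13 points to category 2 and 12.1 to category 1.

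**The case against.** The schedule is consistent across Sections 3.1, 9.1.13, 10 and Appendix 1, which suggests a deliberate choice for a course with nominally 14 days between first and last dose. Visit 6 is not off drug: Table 1 predicts 3.56 to 14.22 ng/mL at 168 hours for 5 to 20 mg/m², so that score is taken under exposure and can inform the MTD. Adverse events are asked about at every visit, parents submit a symptom and seizure diary daily, and the investigator may stop dosing at any time. The DSMB reviews all adverse events before each escalation and before expansion. Nothing forbids an unscheduled C-SSRS. Appendix 1 also names a Dosing Checklist and a Study Continuation Checklist whose contents are not shown and which may already ask about suicidality. The risk basis is thin: the nearest signal is one serious grade 3 mood alteration among 26 participants in the earlier oncology study, at 125 mg/m², which is 125/20 = 6.25 times the top dose here.

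On follow-up, Section 12.3 encourages a final visit with the content of the next scheduled one, so a Visit 6 exit need not lose everything.

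Most of this stands, and it keeps the first part modest. It does not supply the scheduled score on which the listed stopping reason depends. Section 12.3 only encourages one visit and mainly describes voluntary withdrawal. None of it resolves the conflict between 9.1.13 and 12.1, which lies in the protocol's own text.

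**Conclusion.** Both parts hold, as an inexpensive improvement worth considering rather than a flaw in the design. No scheduled post-exposure C-SSRS can inform the decision to give Dose 2 or Dose 3, and the first arrives nominally 21 days after Dose 1 (15-27 without delays). Sections 9.1.13 and 12.1 give different outcomes for the same score. With a first 4 at Visit 6, the literal reading of 9.1.13 costs up to three visits, nominally 83 days and about 23 days of the DLT window, apart from the one withdrawal visit encouraged in 12.3.

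A reader might infer more than the documents support:

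- That suicidality goes unmonitored during dosing. It does not; only the scheduled scale is missing.
- That a 4 obliges the investigator to stop dosing under 12.1. That list is discretionary.
- That the conflict changes the Section 15.4 category for a 4 first seen at Visit 6. Dosing is then complete, so it changes only the study-withdrawal count and the follow-up.
- That the DLT or MTD result is invalid. Nothing here shows that.

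The conclusion rests on post-dosing days being counted from Dose 3 and on the unseen checklists not already containing a suicidality check. The latter affects only the first part. The number of participants affected cannot be estimated, because the documents give no expected rate of suicidal ideation.

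**What to change.** 1. Add a pre-dose C-SSRS at Visits 4 and 5 in Section 9.1.13, Section 10.4 and Appendix 1. If the Dosing Checklist already contains an equivalent check, cite it in 9.1.13 and 10.4 instead.
2. Edit both 9.1.13 and 12.1 to state one rule: a score of 4 or higher ends any remaining ABI-009 dosing, and the participant stays on study for all remaining follow-up visits, including when the score is first seen at Visit 6. Changing 9.1.13 alone would leave the discretionary wording of 12.1 in place.

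The cost is amendment wording plus at most 18 × 2 = 36 short questionnaires at visits that already take place. The documents give no completion time; a few minutes each is assumed. Yield will be limited in the youngest or non-verbal participants, since entry starts at age 3.
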